3.6.1.4 Other Exploratory Analyses

Utility of the SYNTAX score, SYNTAX score II, ACEF score, clinical SYNTAX score, and novel predictive instruments will be investigated.

3.7 FOLLOW-UP TIME POINTS

All subjects will have follow-up as a telephone contact or office visit at 30 ± 7 days, 180 ± 14 days, and at 1, 2, 3, 4 and 5 years (-30days/+60 days). Procedures and tests will be performed at each follow-up time point as per the Schedule of Events within the study protocol. Subjects who have not yet completed the 3-year visit (unless the most recent follow-up was completed within 28 days of the AE check initiation), or who completed the 3 year visit before the lower bound of the 28 day window (i.e. before 1067 days after randomization) will be followed up with a phone call or office visit prior to database snapshot to capture potential withdrawal dates and any events that may have occurred since the last visit. Events dates and early withdrawal date will be collected at this call.

Primary analyses for the study will take place when approximately 50% of the patients have reached the 3-year follow-up AND all patients have reached the 2-year follow-up, whichever time point is latest.

3.8 HANDLING OF MISSING DATA

Every effort will be made to minimize the loss of subjects during this study. Subjects discontinuing early from the study and their reason for dropping out will be summarized by group to see if any biases in the analyses may have been created by any differences between groups.

The impact of missing data will be minimized in the analysis of the primary and key secondary endpoints by performing the analyses using Kaplan-Meier estimates, where subjects will be censored at their last assessed time point.

3.9 Assessment of Data Poolability

3.9.1 Multiple Center Effect

Analyses will be performed pooling data across study sites.

The EXCEL trial will have approximately 165 sites in USA, Canada, Europe, South America, South Korea and Australia, where two treatment strategies (PCI vs CABG) will be compared. Descriptive analysis (number and rate of primary endpoint events) will be performed to assess the consistency of results across sites. For the analysis of center effect, data from smaller sites may be combined by region for the analysis.

3.9.2 Multiple Region Effect

Analyses will be performed pooling data across study regions.

Data will be presented by region, with region being defined by the US, Europe, and outside of US/Europe. Data will also be presented as North America (US/Canada), Europe and outside of NA/EU. To evaluate the potential differences in treatment effect for different regions for the primary and powered secondary endpoints, the interaction p-value from the Cox regression model including region, treatment, and region by treatment interaction term will be compared against a significance level of 0.15.

3.9.3 Multiple Study Stent Effect

The two study stents are considered to be interchangeable in the study and the EXCEL trial is designed to evaluate two treatment strategies (PCI and CABG) instead of any specific study device. To provide evidence for poolability between the two study stents, bioequivalence analysis showing that XIENCE PRIME and XIENCE V are bioequivalent have been submitted to the FDA in the XIENCE PRIME PMA submission (P110019). XIENCE PRIME, XIENCE Xpedition, and XIENCE PRO are the same stent. Descriptive analysis will be performed to assess the consistency of results between the study stents,

3.10 MULTIPLICITY ISSUES

If EXCEL has met the primary analyses of its primary endpoint of the non-inferiority test on the ITT population, additional hypothesis tests for the of the powered secondary endpoints based on the ITT population will be performed following a fixed sequence as below (FWER=family wise error rate). All of these analyses will be performed from time from randomization:

Step 1: Family 1. Primary Endpoint: Death/MI/Stroke at 3 Years PCI non-inferior to CABG (one-sided alpha of 0.025) If passed non-inferiority, PROCEED to Step 2
If failed non-inferiority, STOP

Step 2: Family 2. Major Secondary Endpoint 1: Death/MI/Stroke at 30 Days PCI non-inferior to CABG

(one-sided alpha of 0.05)

If passed non-inferiority, PROCEED to Step 3
If failed non-inferiority, STOP

Step 3: (Simultaneous Testing of 3-1 and 3-2) 3-1. Family 1. Primary Endpoint: Death/MI/Stroke at 3 Years PCI superior to CABG (one-sided alpha of 0.025) 3-2. Family 3. Major Secondary Endpoint 2: Death/MI/Stroke/Revascularization at 3 Years PCI non-inferior to CABG

(one-sided alpha of 0.05)

For hypothesis test(s) of each of the major powered secondary endpoints, the type I error is a 1sided alpha of 0.05. If any hypothesis testing fails in steps 1 and 2, no further testing for the following step will be performed for labeling purposes. However they will still be tested for research and publication purposes. For example, if PCI failed to show non-inferiority to CABG for the major power secondary endpoint of Death/MI/Stroke at 30 Days (step 2), then the hypothesis in step 3 will not be tested for labeling purposes, but may be tested for exploratory reasons. Caution must be exercised when interpreting p-values displayed for analyses other than those performed for the primary and key powered secondary endpoints, as the study was not powered to detect differences on any of those other variables. The resulting p-values, whether or not less-than 0.05, may be a result simply due to chance, and are displayed for hypothesisgenerating purposes only.

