 The primary endpoint will be evaluated using the difference in Kaplan-Meier failure rates in the intent-to-treat population using all available data. The hypothesis test is designed to show non-inferiority of PCI to CABG for the primary endpoint with a one-sided alpha of 0.025. Assuming the following: primary endpoint event rate is 11% in each treatment arm at 3 years (using 3-year event rates from the SYNTAX trial, the most contemporary reference dataset) minimum time to follow-up is approximately 3 years median time to follow-up at 3 years non-inferiority margin Δ = 4.2% one-sided alpha = 0.025 accrual time of 29 months then a sample size population of 1900 subjects (~950 per arm) will provide 80% power to demonstrate non-inferiority. If non-inferiority is met, superiority testing will be performed with a one-sided alpha of 0.025. The trial will have 80% power to demonstrate superiority with a difference of 3.84% of PCI arm to CABG arm (e.g. 7.16% in PCI arm vs. 11% in CABG arm). 		The study is powered for sequential non-inferiority and superiority testing. If the non-inferiority of PCI to CABG test is met for the primary endpoint, then superiority testing will be performed.
 Assuming the following: primary endpoint event rate is 11% in each treatment arm at 3 years (using 3-year event rates from the SYNTAX trial, the most contemporary reference dataset) minimum time to follow-up is years median time to follow-up is approximately 3 years 8% lost to follow-up at 3 years non-inferiority margin Δ = 4.2% one-sided alpha = 0.025 accrual time of 29 months then a sample size population of 1900 subjects (~950 per arm) will provide 80% power to demonstrate non-inferiority. If non-inferiority is met, superiority testing will be performed with a one-sided alpha of 0.025. The trial will have 80% power to demonstrate superiority with a difference of 3.84% of PCI arm to CABG arm (e.g. 7.16% in PCI arm vs. 11% in CABG arm). 		The primary endpoint will be evaluated using the difference in Kaplan- Meier failure rates in the intent-to-treat population using all available data. The hypothesis test is designed to show non-inferiority of PCI to CABG for the primary endpoint with a one-sided alpha of 0.025.

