For the PCI arm to pass the non-inferiority test for the primary endpoint of the composite of death, MI and stroke at 3 years, the maximum allowable event rate would be approximately 12.1%. Comparing to the 11% event rate of the CABG arm, the average difference per year is only $\sim 0.4\%$. The criteria for an acceptable non-inferiority delta has been carefully considered by the principal investigators, executive committee, PCI and surgical committees and country leaders of this protocol, representing more than 100 physicians not related to the study Sponsor, 50% of whom are interventional cardiologists and 50% of whom are cardiac surgeons. A non- inferiority margin of 4.2% for the primary endpoint in this protocol has been agreed upon by this balanced study leadership to represent clinical therapeutic interchangeability⁷⁶ between PCI and CABG, given the substantially lower peri-procedural morbidity of PCI, the likelihood for fewer strokes with PCI, especially in the first 30 days to 1 year (which in most cases is a clinically more important endpoint than MI, although the trial will not be powered to demonstrate a reduction in stroke), and the likely higher rate of subsequent unplanned revascularization for PCI.

If non-inferiority is met, superiority testing will be performed with a one-sided alpha of 0.025.

The null (H_0) and alternative (H_A) hypotheses for the superiority test are:

H₀: $F_{PCI-PE}(T) - F_{CABG-PE}(T) \ge 0$

H_A: $F_{PCI-PE}(T) - F_{CABG-PE}(T) < 0$.

Using a one-sided alpha of 0.025, assuming 8% lost to follow-up at 3 years, the trial will have approximately 80% power to demonstrate superiority with a difference of 3.84% of PCI arm to CABG arm (e.g. 7.16% in PCI arm vs. 11% in CABG arm).

9.1.6.2. Major Powered Secondary Endpoints *Composite of All-Cause Mortality, MI, or Stroke (mRS≥1 and increase by ≥1baseline) at 30 Days*

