9.1.7. Statistical Analysis

9.1.7.1. Analysis of Primary and Major Powered Secondary Endpoints

The primary and the two major powered secondary endpoints will be analyzed for the intentto-treat population, the as-treated population and the per-protocol population. Formal hypothesis testing will be based on the intent-to-treat population. Hierarchical testing will be employed following the order below:

- Primary endpoint-All cause mortality, MI or Stroke from randomization to median follow-up of 3 years (non-inferiority)
- First major powered secondary endpoint-All cause mortality, MI or Stroke from randomization to 30 days
- Second major powered secondary endpoint-All cause mortality, MI, Stroke or Unplanned Revascularization for Ischemia from randomization to median of 3 years
- Primary endpoint All cause mortality, MI, or stroke from randomization to median follow-up of 3 years (superiority)

Formal hypothesis testing of the first major powered secondary endpoint will occur only if noninferiority for the primary endpoint is met. Simultaneous formal hypothesis testing of the second major powered secondary endpoint and the superiority test of the primary endpoint will occur only if non-inferiority for the first major powered secondary endpoint is met.

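### The protocol and SAP each give two rules for when PCI superiority may be tested, and SAP 3.3 implies a different alpha for the second powered secondary endpoint

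*SAP*

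**What the plan says.** **When superiority is tested.** Three passages attach one condition. The Statistical Method part of the Protocol Summary says "If the non-inferiority of PCI to CABG test is met for the primary endpoint, then superiority testing will be performed". Protocol 9.1.6.1 says "If non-inferiority is met, superiority testing will be performed with a one-sided alpha of 0.025", and SAP 2.5.1 repeats that sentence.

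Two passages attach a second condition. The paragraph under the list in protocol 9.1.7.1 allows formal testing of superiority only once non-inferiority at 30 days is met, at the same time as the second powered secondary. SAP 3.10 has the same rule, "following a fixed sequence as below (FWER=family wise error rate": Step 1 is primary non-inferiority, Step 2 is 30-day non-inferiority, and then comes "Step 3: (Simultaneous Testing of 3-1 and 3-2", where 3-1 is superiority at 0.025 and 3-2 is the second secondary at 0.05. After a failed step, "If any hypothesis testing fails in steps 1 and 2, no further testing for the following step will be performed for labeling purposes".

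The list in 9.1.7.1, introduced by "Hierarchical testing will be employed following the order below", puts superiority fourth, after the second secondary. The paragraph below it makes those two items simultaneous.

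**Alpha of the second secondary.** Protocol 9.1.6.2, SAP 2.3.2 and SAP 2.5.2 give one-sided 0.05. SAP 3.10 gives it in Step 3-2 and as a general rule: "For hypothesis test(s) of each of the major powered secondary endpoints, the type I error is a 1sided alpha of 0.05". SAP 3.3 describes the analysis as that of the primary endpoint with only the margin changed to 8.4%. The primary runs at 0.025. The preceding bullet in 3.3, for the 30-day endpoint, does list 0.05 as a difference from the primary.

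**The concern.** A testing hierarchy should give one decision for any data set. Here two results can be read two ways.

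- Primary non-inferiority passes, 30-day non-inferiority fails, and the 3-year superiority test gives p below 0.025. The ungated sentences make this a formal superiority result. Protocol 9.1.7.1 and SAP 3.10 do not.
- The second secondary is tested and its one-sided p lies between 0.025 and 0.05. It passes under SAP 3.10 and fails under SAP 3.3.

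The trial is unblinded (SAP 2.8), so which rule applies should be settled before results are seen.

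**Working it through.** **Inputs** (protocol 9.1.6; SAP 2.5): 950 per arm; 8% lost at 3 years, so 950 × 0.92 = 874 per arm; primary rate 11%, margin 4.2%, alpha 0.025; superiority alternative 7.16% versus 11%; 30-day rate 3%, margin 2%, alpha 0.05; second secondary rate 22%, margin 8.4%. Protocol 9.1.6.2 calls 30-day loss minimal, so 950 per arm is used at 30 days.

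**Formula.** Power = Φ((margin − true difference)/SE − z), with SE = √(p₁(1−p₁)/n + p₂(1−p₂)/n) and the margin set to 0 for superiority.

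**The plan's own figures reproduce:**
- Primary non-inferiority: SE 0.01497; 0.042/0.01497 − 1.960 = 0.846; power 80.1% (stated 80%).
- Superiority: SE 0.01371; 0.0384/0.01371 − 1.960 = 0.840; power 80.0% (stated 80%).
- 30-day non-inferiority: SE 0.00783; 0.02/0.00783 − 1.645 = 0.910; power 81.9% (stated about 80%).
- Second secondary: SE 0.01982; 0.084/0.01982 = 4.239; power 99.5% at 0.05 and 98.9% at 0.025 (stated 99%). The stated power fits either alpha, so it cannot show which was meant.

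**Effect of the 30-day gate on superiority.** The 30-day events are a subset of the 3-year events, so the two tests are positively correlated. Multiplying the powers (0.800 × 0.819 = 0.655) would understate the joint power. Simulating nested outcomes, 950 per arm at 30 days and 874 at 3 years, at least 400,000 trials per scenario, with 7.16% versus 11% at 3 years:

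| 30-day rates, PCI / CABG (assumed) | Superiority, no gate | Superiority, with gate |
|---|---|---|
| 3% / 3% | 80% | about 71% (70.6%) |
| 2.5% / 3% | 80% | about 78% |
| 2% / 3% | 80% | about 80% |

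At 3%/3%, between 9.6% and 9.7% of trials win superiority under the ungated sentences and lose formal status under SAP 3.10.

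**Effect of the alpha in SAP 3.3.** With 22% observed in CABG, the largest PCI rate p that passes solves p − 0.22 + z·√(p(1−p)/874 + 0.22 × 0.78/874) = 0.084.
- z = 1.645 (alpha 0.05): p = 27.0%. Check: 0.0502 + 1.645 × 0.02054 = 0.084.
- z = 1.960 (alpha 0.025): p = 26.4%. Check: 0.0439 + 1.960 × 0.02046 = 0.084.

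An observed PCI rate between about 26.4% and 27.0% therefore passes under one reading and fails under the other. The share of trials in which the readings differ is the difference in power:

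| True rates, PCI / CABG | Power at 0.05 | Power at 0.025 | Readings differ |
|---|---|---|---|
| 22% / 22% (planning) | 99.5% | 98.9% | 0.7% |
| 24% / 22% (assumed) | 93.8% | 88.9% | 4.9% |
| 26% / 22% (assumed) | 69.5% | 57.8% | 11.8% |

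**The case against.** The strongest reply is that the two passages written to set the testing order, the text of 9.1.7.1 and SAP 3.10, agree. The ungated sentences stand in a synopsis and in sample-size sections, and may name only the first condition. Likewise 0.05 is stated in four sections, while 0.025 arises only by inference from SAP 3.3. This makes the intended rule easy to identify. It does not remove the conflict: the ungated sentences say that superiority testing will be done, with no further condition, and neither document says which section governs. SAP 3.3 is the analysis instruction for this endpoint, and it names the alpha change for one secondary but not for the other.

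A reader might infer more. The documents do not support the following:

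- **That superiority must wait for the second secondary to pass.** The list order suggests it, but the paragraph under the list makes the two tests simultaneous. The list only needs aligning.
- **That Step 3 breaks its error control.** One could add 0.025 and 0.05 and report 7.5%. SAP 3.10 labels three families and gives each test its alpha, and each family keeps that alpha. Stating that control is per family would help, but its absence is not an error.
- **That the status of superiority after a failed 30-day test is left open within SAP 3.10.** It says of the later tests "However they will still be tested for research and publication purposes", but its example calls such testing exploratory, and 9.1.7.1 makes formal testing conditional.
- **That the stated powers are wrong.** Quoting power for each hypothesis is ordinary practice. The 71% also assumes no PCI advantage at 30 days, whereas protocol 9.1.6.1 expects lower peri-procedural morbidity and probably fewer early strokes with PCI.

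**Conclusion.** Wrong as written on two points, with limited effect. First, the condition for testing superiority differs between sections of each document. The gate costs about 9 points of superiority power (80% to 71%) if 30-day rates are equal at 3%, and almost nothing at 2% versus 3%. Second, SAP 3.3 conflicts with the 0.05 given elsewhere for the second secondary. The results it separates are rare at planning rates and become more common as the PCI composite rate rises.

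The sizes rest on the plan's 3-year rates, 874 per arm at 3 years and 950 at 30 days, nested endpoints, normal-approximation tests, and the assumed 30-day and composite rates shown in the tables. Primary non-inferiority and study success (SAP 2.7) do not depend on either point.

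**What to change.** **Required wording changes**
- In the Protocol Summary, protocol 9.1.6.1 and SAP 2.5.1, say that superiority is tested only if both primary non-inferiority and 30-day non-inferiority are met.
- In the 9.1.7.1 list, mark items 3 and 4 as simultaneous.
- In SAP 3.3, write one-sided 0.05 for the second powered secondary.
- Beside the 80% superiority power, note that it is before the 30-day gate.

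**Optional clarifications, not corrections of error**
- In SAP 3.10, say that type I error is controlled within each family, and that Step 3 results after a failed gate are exploratory in publications as well as for labeling.
- In SAP 3.2, run the Cox superiority sensitivity analysis at one-sided 0.025, like the test it supports. It is now set at 0.05.

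**Cost.** Text only. Sample size, data collection, the primary alpha and the 0.05 for the second secondary stay as they are. The one drawback is a less favourable description of superiority power.

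### SAP 3.10 lets the two powered secondary non-inferiority tests go to publication at full nominal alpha after the testing sequence has stopped

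*SAP*

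**What the plan says.** SAP 3.10 lays out three steps on the ITT population. Step 1 is primary non-inferiority: "PCI non-inferior to CABG (one-sided alpha of 0.025"). Step 2 is 30-day non-inferiority. Step 3 tests primary superiority (one-sided 0.025) and non-inferiority on the composite with revascularization at the same time. For each powered secondary endpoint, "the type I error is a 1sided alpha of 0.05". A failure at Step 1 or Step 2 is marked as a stop.

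The paragraph below the steps then narrows that stop: "no further testing for the following step will be performed for labeling purposes". The next sentence reads "However they will still be tested for research and publication purposes". The worked example after it, about a failed 30-day test, says that Step 3 will not be tested "for labeling purposes, but may be tested for exploratory reasons". The paragraph closes with a caution that p-values are only hypothesis-generating, but restricts it to "analyses other than those performed for the primary and key powered secondary endpoints".

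Protocol 9.1.7.1 has one hierarchy and makes no distinction between labeling and publication: "Formal hypothesis testing of the first major powered secondary endpoint will occur only if" primary non-inferiority is met. The second secondary endpoint and superiority likewise depend on the 30-day result. SAP section 5, which lists changes from the protocol, mentions only the as-treated population and the Kaplan-Meier form of the 30-day endpoint.

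**The concern.** After a failed step the SAP gives the later powered tests two statuses. They are to be done and are meant for publication, and they are also optional and exploratory. Nothing else in the SAP settles which applies:

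- SAP 3.4.4 describes the tests of the primary and powered secondary endpoints as formal. Its decision rule declares non-inferiority whenever the upper confidence bound lies below the margin, with no condition on the sequence. It refers to the endpoint sections for details, and SAP 3.3 does not mention the gates either.
- The cautions in SAP 3.4.4 and 3.10 both exempt the primary and powered secondary endpoints.

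Following the SAP as written, a paper could therefore state that PCI is non-inferior at 30 days, or non-inferior on the composite with revascularization, each at one-sided 0.05, after the gate protecting that claim had failed. Protocol 14.1 commits the trial to publication whatever the findings, so this is a main route by which the results will be used. The trial is also unblinded, which is a reason to settle the status of these tests before results are known.

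**Working it through.** **Inputs.** Levels from SAP 3.10: 0.025 (primary non-inferiority), 0.05 (30-day), 0.05 (revascularization composite), 0.025 (superiority). Planning rates and margins from SAP 2.5: 11% and 4.2 points, 3% and 2 points, 22% and 8.4 points. There are 950 subjects per arm and 8% loss at 3 years, which leaves 950 × 0.92 = 874.

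**The plan's own figures.** The documents state no overall error rate, so the check is that the stated levels reproduce the stated power, using Φ(margin / √(2p(1−p)/n) − z).
- Primary: √(2 × 0.11 × 0.89 / 874) = 0.01497; 0.042 / 0.01497 = 2.806; 2.806 − 1.960 = 0.846; power 80.1% (stated: about 80%).
- 30-day, n = 950: 0.02 / 0.00783 = 2.555; 2.555 − 1.645 = 0.910; power 81.9% (stated: about 80%).
- Revascularization composite, n = 874: 0.084 / 0.01982 = 4.239; 4.239 − 1.645 = 2.594; power 99.5% (stated: about 99%).

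**Superiority adds nothing to the primary pair.** SAP 2.3.1 uses the same estimate and standard error for both primary tests and only removes the margin. Any result that rejects for superiority at 0.025 therefore also rejects for non-inferiority at 0.025. Superiority cannot be claimed after a failed Step 1, and the pair's error stays at 0.025 even if the 30-day gate is ignored (simulated: 0.0249).

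**Bounds with the gates enforced.**
- Primary non-inferiority false: any false claim must first pass Step 1, so at most 0.025.
- Primary non-inferiority true, 30-day false: at most 0.05.
- Both true, Step 3 nulls true: 0.025 + 0.05 = at most 0.075.

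**Bound with the gates not applied.** 0.025 + 0.05 + 0.05 = 0.125. If independent: 1 − 0.975 × 0.95 × 0.95 = 0.120.

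**Correlated values.** Treating the composites as nested at the planning rates, the correlation is √[a(1−b) / (b(1−a))] for a < b. This gives 0.50 (3% with 11%), 0.66 (11% with 22%) and 0.33 (3% with 22%). A normal simulation with 4 million draws gives:

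| True state | Gates enforced | Gates not applied |
|---|---|---|
| All three non-inferiority nulls at their margins | 0.025 | 0.102 |
| Primary difference 0; 30-day and revascularization composites at their margins | 0.049 | 0.102 |
| Primary and 30-day differences 0; revascularization composite at its margin | 0.061 | 0.064 |

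With one common correlation in place of the derived ones, the ungated value in the first two rows is 0.120 at 0, about 0.10 at 0.5 and 0.070 at 0.9. In the first row, 0.102 − 0.025 = 0.077 of trials fail Step 1 and still give at least one nominally positive powered secondary result. The range is 0.070 − 0.025 = 0.045 to 0.120 − 0.025 = 0.095.

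**The case against.** The strongest reply is that this is loose wording rather than a licence to claim. SAP 3.10 marks a stop after Steps 1 and 2, its only worked example says "but may be tested for exploratory reasons", and being tested is not the same as being declared. Protocol 9.1.7.1 restricts only formal testing. The same section has the endpoints analysed in three populations but formally tested in one, so informal analysis of these endpoints is foreseen.

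Part of this stands. A reader might infer that the SAP contradicts the protocol. The documents do not establish that, because the later tests can be read as informal. What they show is a departure that is not declared in SAP section 5 and not reconciled with SAP 3.4.4.

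Three other inferences go too far.
- *Published claims have no family-wise error control.* The split operates only after a failure. If Steps 1 and 2 pass, the published and labeling tests are the same. Primary non-inferiority, on which SAP 2.7 bases study success, is always tested at 0.025.
- *A superiority claim is exposed.* It is nested in primary non-inferiority, as shown above. Protocol 9.1.6.1 and SAP 2.5.1 also allow it directly after primary non-inferiority.
- *The error is multiplied about fourfold in general.* That ratio (0.102 / 0.025) belongs to the state in which the gate performs best. In the second row of the table it is about two (0.102 / 0.049), and in the third there is almost no difference.

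The reply does not remove the defect: the sentence on publication, the unconditional decision rule and the exempting cautions together leave two powered claims open after a failed gate.

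**Conclusion.** The point holds for the two powered secondary non-inferiority claims, each at one-sided 0.05. As written, the SAP lets them be published at nominal alpha after the sequence has stopped.

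The fair overall comparison is of worst cases: at most 0.075 with the gates enforced against at most 0.125 without them (0.120 if independent, about 0.10 at correlation 0.5). In the least favourable state for primary non-inferiority, the rise is from 0.025 to about 0.10 (0.07 to 0.12). The two bounds need no assumption about correlation. The intermediate values assume normal test statistics and, where derived, nested composites at the planning rates.

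Enforcing the gates does not bring every state down to 0.025 or 0.05, because Step 3 tests at both levels together with no split of alpha.

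**What to change.** In SAP 3.10:
- State that the sequence governs claims in all reports, including publications.
- State that after a failed step the remaining powered secondary endpoints are reported as estimates with confidence intervals, labelled exploratory, with no statement of non-inferiority.
- Remove the conflict between mandatory and optional testing.

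Extend the cautions in SAP 3.4.4 and 3.10 to powered endpoints that lie after a failed step. If any difference between labeling and publication is kept, list it in SAP section 5.

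Separately, reconcile the two rules for superiority. Protocol 9.1.6.1 and SAP 2.5.1 allow it once primary non-inferiority is met; protocol 9.1.7.1 and SAP 3.10 require the 30-day result as well. Either rule keeps the primary pair at 0.025, but only one can apply.

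The cost is a few sentences, with no new data or analysis. The downside is that no powered secondary non-inferiority claim can be published after a failed gate. Readers could still compare a reported confidence limit with the margin, so the gain lies in what the trial claims, not in what it discloses. The Step 3 bound of 0.075 is unchanged.
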